#### **8.4.2 Stopping rules related to the CNS3 cohort**

Accrual to the CNS3 cohort will be stopped for review if:

- 1) Any subject develops a grade 5 neurological toxicity attributable to CART-19 infusion.
- 2) Any subject develops grade 3/4 neurotoxicity or agitation, confusion, delirium, or psychosis (psychiatric) toxicity that has not resolved to  $\leq$  Grade 2 within 4 weeks with or without medical intervention (ie: anti-epileptics).
- 3) Any non-resolving grade 3 or 4 neuro toxicity or death due to neuro/psychiatric toxicity clearly attributable to the CART cells will lead to a hold on any further CNS3 patients enrolled in this high risk stratum pending subsequent review.

CONFIDENTIAL

Note on attribution: Toxicity is attributable to CART-19 infusion if, in the opinion of the principal investigator or sponsor, the event was more likely than not to be caused by the CART-19 cells. In making this determination, the investigator will assess:

- Timing (most other toxicities, other than cytopenias and hypogammaglobulinemia are resolved within 28 days of infusion).
- Predisposing structural CNS lesions, prior strokes, or prior seizure history
- Neurologic baseline at study entry
- Events during CRS that may have been predisposing to CNS toxicity (such as significant coagulopathy)
- Infections are most likely attributable to cytopenias due to disease and chemotherapy, and are therefore less likely to be due to CART-19 infusion

#### 8.4.3 General toxicity management considerations

- Replication-competent lentivirus (RCL) may be generated during the CART-19 manufacturing phase or subsequently after introduction of vector transduced cells into the patient. However, an RCL resulting from the production phase is highly unlikely since elements are incorporated in the design of the vector system that minimize vector recombination and generation of RCL. Furthermore, the vector used to transduce the product undergoes sensitive assays for detection of RCL before it can be released to a subject. Nevertheless, generation of an RCL following infusion of the vector product remains a theoretical possibility. The consequences of such recombination events in subjects without a known lentiviral infection are unknown, and therefore subjects with coexistent HIV infection are excluded from participation in this study in order to minimize this possibility. The development of RCL could pose a risk to both the subject and their close contact(s), and therefore, monitoring for RCL will be conducted during the course of the trial.

Regulatory agencies and the gene therapy community have previously discussed measures to be taken should an RCL be confirmed in a subject. However, because the probability and characteristics of an RCL are unknown, no guidelines have been put in place. Nevertheless, all agree that the subject must be isolated until an understanding of how to manage the subject becomes clear. Some considerations are

- Intensive follow-up of subject in consultation with gene therapy experts, study investigators, FDA and NIH.
  - Inform local public health officials and CDC.
  - Identify sexual partners and provide appropriate counseling and intervention.
- RCL Testing: If a positive RCL assay result is obtained from a subject blood specimen, the PI will be informed and the subject rescheduled for a retest for the DNA test. If the second RCL test is positive, then infusions will be temporarily halted. The patient will undergo a blood draw for isolation of HIV from his/her cells. The virus will be sequenced and compared to sequences of the transfer vector and packaging constructs, as well as to available HIV sequences to determine the origin of the virus. Determination of the origin of the virus can be easily performed by evaluation for HIV accessory genes such as vif, vpr and vpu which are not present in the packaging constructs. If the sequence is derived from wt-HIV then infusions for all subjects can

CONFIDENTIAL

resume, and the patient will be referred to treatment for HIV. If an RCL is confirmed, or the virus cannot be isolated from the blood draw, the patient will be scheduled for apheresis and will undergo a full biological RCL testing for detection and/or characterization of the RCL.

- Clonality and insertional oncogenesis: The occurrence of adverse events caused by insertional mutagenesis in three patients in a gene therapy trial for X-linked SCID following stem cell therapy emphasizes the potential for problems in translating this approach to the clinic. To date, clinically evident insertional mutagenesis has not been reported following adoptive of engineered T cells. Lentiviral vectors may have a lower risk than oncoretroviral vectors based on several considerations. Monitoring for T cell clonal outgrowth will be performed by flow cytometric analysis for T-body-expressing cells, and by CBC count. If the number of chimeric immune receptor cells continues to increase after 6 weeks, a V $\beta$  repertoire analysis will be performed to evaluate clonality, or if the CBC analysis reveals abnormal T cell counts, then the V $\beta$  analysis will be performed earlier. If a subject's V $\beta$  repertoire is found to be monoclonal or oligoclonal, the subject's T cells will be evaluated for the pattern of vector insertion. If the pattern of insertion is found to favor a single dominant insertion site pattern the clinical trial will be placed on hold for dosing to allow evaluation of the subject in consultation with gene therapy experts, study investigators, DSMB, FDA and NIH. Further evaluation of the subject will comprise confirmation of the persistence of the clonality within a 3 month period, and monitoring of the subject for hematologic malignancies. Optionally, a sequence analysis of the dominant insertion site(s) will be performed, in order to locate any association of the insertion sites with known human oncogenes.
- Uncontrolled T cell proliferation. CART-19 T cells could proliferate without control of normal homeostatic mechanisms. In pre-clinical studies, CART-19 cells have only proliferated in response to physiologic signals or upon exposure to CD19. In the context of this protocol it is possible that the T cells will proliferate in response to signals from the malignant tumor or normal B cells. This could be beneficial or harmful depending on the extent of proliferation. Clonal dominance of adoptively transferred T cells has been associated with tumor reduction in adoptive transfer trials. If any subject develops excessive CART-19 T cell accumulation, corticosteroids will be administered to eradicate the infused cells.

#### **8.4.4 Management of toxicity**

Uncontrolled T cell proliferation. Toxicity associated with allogeneic or autologous T cell infusions has been managed with a course of pharmacologic immunosuppression. T body associated toxicity has been reported to respond to systemic corticosteroids. If uncontrolled T cell proliferation occurs, subjects will be treated with corticosteroids. Subjects will be treated with pulse methylprednisolone (2 mg/kg i.v. divided q6-8 hr x 2 days), followed by a rapid taper.

Recommended treatment of cytokine release/ possible macrophage activation syndromes. Given the dramatic clinical improvement of several of the patients treated on this protocol after treatment with anti-cytokine therapy, we will prospectively manage potential cytokine toxicities

CONFIDENTIAL

with tocilizumab (anti-IL-6), with or without other agents such as steroids and etanercept (anti-TNF $\alpha$ ). This management approach is designed to avoid life-threatening toxicities, while attempting to allow the CART-19 cells to establish the proliferative phase that appears to correlate with anti-tumor efficacy. Thus, the timing of the interventions below will be individualized in close consultation with the admitting service.

- Subjects will be treated with tocilizumab (CHOP Formulary dose 8 mg/kg, or 12mg/kg for patients <30kg, as per the package insert) with or without corticosteroids if grade 4 toxicity related to CART-19 cells is observed, such as hypoxia, respiratory distress, or hypotension. If possible and when used, steroids will be rapidly tapered.
- Subjects who have not responded to tocilizumab may be treated with a single dose of etanercept (CHOP Formulary dose 0.8mg/kg) if they have developed significant respiratory distress including intubation.
- Subjects will be treated with a single dose of tocilizumab (as above) if they develop hypotension requiring more than low-dose pressor support.

Events of Cytokine Release Syndrome (CRS) will be reported and graded based on the below criteria for all patients that experience CRS moving forward. Events prior to this amendment will be reviewed and retrospectively be graded and reported by the primary investigator per source documentation. The Penn Grading Scale for Cytokine Release Syndrome (PGS-CRS) will be used for grading of CRS. Please see below for details.

#### **CTL019-Therapy-Associated Grading for Cytokine Release Syndrome: The Penn Grading Scale for Cytokine Release Syndrome (PGS-CRS)**

- Marked elevations in IL-6, interferon gamma and less intensely TNF
- Symptoms occur 1 to 14 days after cell infusion in ALL
- Symptoms may include: High fevers, rigors, myalgia, arthralgia, nausea, vomiting, anorexia, fatigue, headache, hypotension, encephalopathy, dyspnea, tachypnea, and hypoxia
- The start date of CRS is a retrospective assessment of the date of onset of persistent fevers and/or myalgia consistent with CRS and not explained by other events (i.e. sepsis). The stop date of CRS is defined as the date when the patient has been afebrile for 24 hours and off vasopressors for 24 hours.

CONFIDENTIAL

**Table 8-1**

1	2	3	4	5

Mild reaction: Treated with supportive care such as anti-pyretics and anti-emetics.
	
Moderate reaction: Requiring intravenous therapies or parenteral nutrition; some signs of organ dysfunction (i.e. grade 2 creatinine or grade 3 liver function tests [LFTs]) related to CRS and not attributable to any other condition. Hospitalization for management of CRS related symptoms including fevers with associated neutropenia.
	
More severe reaction: Hospitalization required for management of symptoms related to organ dysfunction including grade 4 LFTs or grade 3 creatinine related to CRS and not attributable to any other conditions; this excludes management of fever or myalgias. Includes hypotension treated with intravenous fluids* or low dose pressors, coagulopathy requiring fresh frozen plasma (FFP) or cryoprecipitate, and hypoxia requiring supplemental oxygen (nasal cannula oxygen, high flow oxygen, Continuous Positive Airway Pressure [CPAP] or Bilateral Positive Airway Pressure [BiPAP]). Patients admitted for management of suspected infection due to fevers and/or neutropenia may have grade 2 CRS.
	
Life-threatening complications such as hypotension requiring high dose pressors (see Table 8-2) or hypoxia requiring mechanical ventilation.
	
Death

*Defined as: multiple fluid boluses for blood pressure support.
				

CONFIDENTIAL

**Table 8-2 High Dose Vasopressor Use**

Definition of “High-Dose” Vasopressors	
Vasopressor	Dose for $\geq 3$ hours
Norepinephrine monotherapy	$\geq 0.2$ mcg/kg/min
Dopamine monotherapy	$\geq 10$ mcg/kg/min
Phenylephrine monotherapy	$\geq 200$ mcg/min
Epinephrine monotherapy	$\geq 0.1$ mcg/kg/min
If on vasopressin	High-dose if vaso + Norepinephrine Equivalent (NE) of $\geq 0.1$ mcg/min (using Vasopressin and Septic Shock Trial (VASST) formula)
If on combination vasopressors (not vasopressin)	Norepinephrine equivalent of $\geq 20$ mcg/min (using VASST formula)

Vasopressin and Septic Shock Trial (VASST) Equivalent Equation:                      Norepinephrine equivalent dose = [norepinephrine (mcg/min)] + [dopamine (mcg/kg/min) <math>\div</math> 2] + [epinephrine (mcg/min)] + [phenylephrine (mcg/min) <math>\div</math> 10]                      Criteria from Russell et al 2008.
 
Note: Pediatric weight adjustments should be taken into consideration.
	

B cell depletion. It is likely that B cell depletion and hypogammaglobulinemia will occur in CART-19 patients who have a disease response. This is common with anti-CD20 directed therapies. In the event of clinically significant hypogammaglobulinemia (i.e. systemic infections), subjects will be given intravenous immunoglobulin (IVIG) by established clinical dosing guidelines to restore normal levels of serum immunoglobulin levels, as has been done with Rituximab.

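### Table 8-2: the vasopressin row's threshold of 0.1 mcg/min does not fit the other rows, so vasopressin plus a minimal second pressor for 3 hours reads as grade 4 CRS

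*Combined protocol and SAP*

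**What the plan says.** Section 8.4.4 adopts the Penn scale for CRS: "Events of Cytokine Release Syndrome (CRS) will be reported and graded based on the below criteria". It applies the scale to all later events and asks for earlier events to be graded retrospectively from source documents.

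In Table 8-1, grade 4 covers "Life-threatening complications such as hypotension requiring high dose pressors", with a pointer to Table 8-2. Hypotension managed with fluids or low-dose pressors is grade 3.

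Table 8-2 defines high-dose, and its column header requires the dose to last at least 3 hours:

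- **Single agents:** norepinephrine 0.2 mcg/kg/min, dopamine 10 mcg/kg/min, phenylephrine 200 mcg/min, epinephrine 0.1 mcg/kg/min (each as a minimum).
- **Vasopressin row:** "High-dose if vaso + Norepinephrine Equivalent (NE) of" at least 0.1 mcg/min, by the VASST equation.
- **Row beginning** "If on combination vasopressors (not vasopressin": a norepinephrine equivalent of at least 20 mcg/min, by the same equation.

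The equation adds norepinephrine (mcg/min), dopamine (mcg/kg/min) divided by 2, epinephrine (mcg/min) and phenylephrine (mcg/min) divided by 10. Vasopressin is not a term. A note under the table asks for pediatric weight to be considered but gives no rule.

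**The concern.** Two rows use one equation and differ by a factor of 200. Because vasopressin contributes nothing to the equation, the 0.1 mcg/min has to come entirely from the other agents. A figure that small is reached by almost any running infusion of a second pressor, so the row in effect says vasopressin plus anything, while presenting itself as a dose cut-off.

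The grade 3/4 split of CRS is at stake. Two graders, one applying the row as printed and one taking the unit as a slip, would grade the same patient differently, both prospectively and in the retrospective review. Section 8.4.4 also attaches management to grade 4 toxicity and to hypotension needing pressor support above low dose. Low dose is not defined separately, so the row may reach those conditions as well.

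**Working it through.** **Inputs.** All thresholds and the equation come from Table 8-2. Body weight is an assumption: Section 4.1 gives ages 1 to 24 years but no weights are stated, so 10 to 70 kg is used. The 6 kg apheresis limit in Section 1.4 and 80 kg serve as outer checks.

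**Step 1: combination row against vasopressin row.** Same equation, same unit, no weight needed: 20 / 0.1 = 200.

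**Step 2: put each row on the norepinephrine-equivalent scale and divide by 0.1.** Per-kg thresholds for norepinephrine and epinephrine are multiplied by weight. Dopamine is 10 / 2 = 5 and phenylephrine is 200 / 10 = 20, at any weight.

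| Row | Equivalent at 10 kg | Equivalent at 70 kg | Multiple of 0.1 | 0.1 as a share of the row |
|---|---|---|---|---|
| Norepinephrine alone | 0.2 × 10 = 2 | 0.2 × 70 = 14 | 20 to 140 | 5% to 0.7% |
| Epinephrine alone | 0.1 × 10 = 1 | 0.1 × 70 = 7 | 10 to 70 | 10% to 1.4% |
| Dopamine alone | 5 | 5 | 50 | 2% |
| Phenylephrine alone | 20 | 20 | 200 | 0.5% |
| Combination without vasopressin | 20 | 20 | 200 | 0.5% |

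The four single-agent rows together are 10 to 200 times higher. At 6 kg the norepinephrine multiple is 12 and the epinephrine multiple is 6 (0.1 is about 17% of that row). At 80 kg the norepinephrine multiple is 160.

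**Step 3: the dose of a second agent that meets the vasopressin row.**

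- Norepinephrine or epinephrine: 0.1 / 10 = 0.01 mcg/kg/min at 10 kg, and 0.1 / 70 = 0.0014 mcg/kg/min at 70 kg.
- Dopamine: 0.1 × 2 = 0.2 mcg/kg/min.
- Phenylephrine: 0.1 × 10 = 1 mcg/min.

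**Step 4: a worked child of 20 kg.** On norepinephrine alone at 0.19 mcg/kg/min (3.8 mcg/min), the child is below the single-agent threshold and not high-dose. On vasopressin plus norepinephrine at 0.005 mcg/kg/min (0.1 mcg/min), held for 3 hours, the child is high-dose and therefore grade 4.

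**The case against.** The strongest reply is that the factor of 200 is not the size of an error. The equation ignores vasopressin, so the row counts only what is given on top of it, and a lower threshold than in the vasopressin-free row is to be expected. How much lower depends on the cited source, which is not among the 132 numbered references in Section 14. This stands as far as it goes: some reduction is plausible. It does not explain a figure at 0.5 to 10% of each agent's own cut-off. If any second agent was meant to count, the row needs no dose.

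The size also depends on the unit. As a sensitivity check only, and not as a proposed correction, a per-kg unit would make the row half the norepinephrine row at every weight, and the combination row 20 to 2.9 times higher at 10 to 70 kg. The norepinephrine, dopamine and epinephrine rows do carry a per-kg unit in the same text, so loss of the symbol from this row alone is unlikely, but the printed page should be checked. The pediatric note does not help: scaling a fixed mcg/min figure down for a small child would lower it further.

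The consequences are limited, and several stronger readings are not supported:

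- **That everyone given vasopressin becomes grade 4.** The row requires a second agent and at least 3 hours. Patients who are ventilated, or whose second agent is at a high dose by its own row, are grade 4 or high-dose already.
- **That vasopressin alone has no class.** Table 8-2 defines only high-dose. Vasopressin alone does not meet the row, so by exclusion it is not high-dose.
- **That the main safety outputs change.** The primary adverse event endpoint (Sections 3.2 and 7.2.1) starts at grade 3, the DLT definition (Section 8.1) covers grades 3 and 4, and the 7-day FDA report (Section 8.3.4) covers CRS of grade 3 or higher. The pause rule (Section 8.4.1) needs grade 4 toxicity that is unmanageable and unexpected, and lists hypotension as expected, so it is little exposed.
- **That the combination row is also wrong.** Nothing here shows that.

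**Conclusion.** The vasopressin row is wrong as written, in the sense that its unit or its figure is inconsistent with the rest of Table 8-2. The 200-fold gap to the combination row needs no assumption. The multiples of 20 to 140 (norepinephrine alone) and about 10 to 200 (all four single-agent rows) assume 10 to 70 kg.

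Followed literally, the row makes hypotension treated with vasopressin plus a minimal dose of a second pressor for at least 3 hours grade 4 rather than grade 3 CRS. The effect is on the reported grade 3/4 split, and possibly on the grade 4 and pressor-support conditions in Section 8.4.4. Section 7 names no analysis of CRS grade, and the documents do not say how many subjects received vasopressin, so the number of grades affected cannot be estimated. The point merits correction because the scale governs both prospective and retrospective grading.

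**What to change.** The sponsor should:

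1. Confirm the unit and figure in the vasopressin row on the printed table and against the source of the scale.
2. Reconcile that row with the other rows of Table 8-2. The value is for the sponsor to supply.
3. Re-check the CRS grade of subjects who received vasopressin together with a second pressor.

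The cost is one table cell and a small addition to the retrospective grading review that Section 8.4.4 already requires.

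### Table 8-2 is not monotone: at an assumed 70 kg, dopamine plus epinephrine (and, narrowly, dopamine plus norepinephrine), each at its own high-dose threshold, misses the combination cut-off

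*Combined protocol and SAP*

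**What the plan says.** Section 8.4.4 adopts the Penn Grading Scale for CRS. Events are to be graded on it from the amendment onward, and earlier events are to be regraded retrospectively from source. In Table 8-1, grade 3 includes hypotension treated with low-dose pressors, a term that the protocol does not define. Grade 4 reads "Life-threatening complications such as hypotension requiring high dose pressors" and refers to Table 8-2.

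Table 8-2 applies one duration to all rows ("Dose for $\geq 3$ hours"). It has three kinds of row:

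- Four rows labelled monotherapy: norepinephrine 0.2 mcg/kg/min, dopamine 10 mcg/kg/min, phenylephrine 200 mcg/min, epinephrine 0.1 mcg/kg/min.
- A row for combinations without vasopressin: "Norepinephrine equivalent of $\geq 20$ mcg/min (using VASST formula".
- A row for patients on vasopressin: "High-dose if vaso + Norepinephrine Equivalent (NE) of $\geq 0.1$ mcg/min".

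The equivalence formula printed below the rows takes dopamine per kg and the other agents in absolute mcg/min. A closing note says "Pediatric weight adjustments should be taken into consideration", with no rule or reference weight. Nothing says that an agent which meets its own threshold inside a combination also counts.

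**The concern.** A severity definition should not rank two pressors at full threshold below one of them alone. Because the single-agent rows are labelled monotherapy and combinations have a row of their own, a literal reader applies only the 20 mcg/min rule to a patient on two agents. Most of the single-agent thresholds are worth well under 20 in the table's own formula, so some pairs of full-threshold doses can fall short. A grader using common sense would call the same patient high-dose. What is at stake is whether hypotensive CRS is graded 3 or 4 in the same way across patients, and across the prospective and retrospective gradings.

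**Working it through.** **Inputs.** The thresholds, the cut-off and the formula are those printed in Table 8-2. Body weight w is not in the documents. I assume 70 kg because section 7.1 says that some adults up to age 24 are enrolled, and I show a range. The 20 mcg/min is a definition, so there is no derived figure to reproduce.

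**Formula.** Norepinephrine equivalent (mcg/min) = norepinephrine (mcg/min) + dopamine (mcg/kg/min)/2 + epinephrine (mcg/min) + phenylephrine (mcg/min)/10.

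**Each agent at its own threshold, 70 kg.**

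- Dopamine: 10/2 = 5
- Epinephrine: 0.1 × 70 = 7
- Norepinephrine: 0.2 × 70 = 14
- Phenylephrine: 200/10 = 20

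Only phenylephrine maps to the combination cut-off.

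**Pairs at threshold against 20, no weight adjustment.**

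| Pair | Formula | 20 kg | 50 kg | 70 kg | 90 kg | Reaches 20 at |
|---|---|---|---|---|---|---|
| Dopamine + epinephrine | 5 + 0.1w | 7 | 10 | 12 | 14 | 15/0.1 = 150 kg |
| Dopamine + norepinephrine | 5 + 0.2w | 9 | 15 | 19 | 23 | 15/0.2 = 75 kg |
| Norepinephrine + epinephrine | 0.3w | 6 | 15 | 21 | 27 | 20/0.3 = 66.7 kg |

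Any pair with phenylephrine starts from 20 and is never short. So two of the six pairs miss at 70 kg. With dopamine at 10 mcg/kg/min, epinephrine would have to reach (20 − 5)/70 = 0.214 mcg/kg/min, which is 2.1 times its own threshold.

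**What the pediatric note could do.** It gives no rule. Two readings, both with an assumed 70 kg reference:

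1. Scale only the cut-off, to 20w/70, since dopamine is already per kg.
   - Dopamine + epinephrine qualifies when 5 + 0.1w ≥ 0.2857w, that is w ≤ 5/0.1857 ≈ 27 kg.
   - Dopamine + norepinephrine qualifies when 5 + 0.2w ≥ 0.2857w, that is w ≤ 5/0.0857 ≈ 58 kg.
   - Norepinephrine + epinephrine always qualifies (0.3w > 0.2857w).
   - At 20 kg the cut-off is 5.7 and all three pairs (7, 9, 6) meet it. At 50 kg it is 14.3 and only dopamine + epinephrine (10) is short.
2. Scale the cut-off and the dopamine term together. The ratios to the cut-off then stay at 12/20 = 0.60 and 19/20 = 0.95 at every weight, so both dopamine pairs remain short.

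The 70 kg result is the same under either reading. The result in small children is not.

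**Vasopressin row.** An added equivalent of 0.1 mcg/min is met by dopamine at 0.2 mcg/kg/min (0.2/2 = 0.1) or phenylephrine at 1 mcg/min (1/10 = 0.1).

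**The case against.** The strongest reply is that little depends on this. A reader might infer that the table distorts the primary safety endpoint or a reporting rule. The documents do not support that:

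- The endpoint in section 3.2 counts events of grade 3 or higher, so a 3/4 split does not move it.
- Expedited FDA reporting of CRS (section 8.3.4) starts at grade 3.
- The pause rule (section 8.4.1) needs an unexpected grade 4 toxicity, and hypotension is listed as expected.
- Tocilizumab for hypotension has its own trigger in section 8.4.4, which does not cite Table 8-2.
- Section 7.7 names no analysis by CRS grade.

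All of this stands.

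A reader might also infer that adding a second pressor downgrades a patient, or that grade 3 is forced. Neither follows. A patient who has completed 3 hours on one qualifying agent has already met a monotherapy row, and no text cancels that. Grade 4 is also an open list, so a grader may assign it outside Table 8-2.

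A third tempting inference is that the problem must be worst in small children. It is larger there only if no weight adjustment is made. Scaling the cut-off alone removes it at low weights, and the protocol does not say which adjustment applies.

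Finally, 0.1 against 20 mcg/min looks like a 200-fold error in the vasopressin row. The formula has no vasopressin term, however, and that row counts only what is given on top of vasopressin, so a lower cut-off is to be expected. The criteria are credited to a publication not available here. The value is worth a query but is not a shown error.

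None of this makes the literal 70 kg reading consistent.

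**Conclusion.** The concern holds in a limited form, and its severity is minor. On the printed table at an assumed 70 kg, dopamine + epinephrine (12) clearly misses 20 mcg/min. Dopamine + norepinephrine (19) misses by 1 and qualifies from 75 kg. Each of these agents alone at the same dose for 3 hours is high-dose. The conclusion rests on the assumed weight and on taking the monotherapy labels literally. Below 70 kg no single size can be given, because the pediatric note has no stated rule.

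The effect is confined to the descriptive grade 3/4 split for CRS hypotension, in patients put on two pressors before completing 3 hours on one qualifying agent. The same such patient can be graded either way. The documents give no counts of pressor combinations, so the number affected is unknown and may be zero.

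**What to change.** Add one sentence to Table 8-2: a subject is high-dose if any single agent meets its own threshold for at least 3 hours regardless of added agents, or if the combination criterion is met. Apply it in both the prospective grading and the retrospective grading already planned.

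As a query only, ask the sponsor to verify the value and unit of the vasopressin row.

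The cost is one sentence and one check. The affected cases can be graded from pressor records already in source, with no new data. The drawback is a small departure from the named scale as printed, which the report should note.
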